9.4. New or Worsening Disease Manifestations

New or worsening manifestation(s) of PM or DM should not be recorded as AEs unless they are assessed as serious.

9.5. Injection Site Reactions

In study participants who have received KZR-616 SC, ISRs, including bruising, discoloration, discomfort, erythema, induration, pain, pruritus and/or swelling, have been described in the majority of participants in KZR-616 studies to date; these events have been predominantly mild. No interventions have been formally studied to prevent or treat these reactions; however, local therapy such as topical antihistamines or corticosteroids may be helpful, and/or systemic antihistamines, anti-inflammatory drugs, and/or corticosteroids may be appropriate in more severe cases.

9.5.1. Adverse Events of Special Interest

An AE of special interest (AESI) is one that is of scientific and medical concern specific to the Sponsor's product or program, for which ongoing monitoring and rapid communication by the Investigator to the Sponsor can be appropriate, regardless of the seriousness, expectedness, or relatedness of the AE to the administration of a product or compound. A complex of tolerability symptoms (formerly referred to as systemic injection reaction; see [Section 9.5.1.1](#)) and thrombotic microangiopathy have been identified as AESIs, and should be reported within 24 hours using the AE eCRF.

9.5.1.1. Tolerability Symptom Complex

Initial SC doses of 60 mg KZR-616 are associated with a complex of tolerability symptoms, with at least one of the following signs or symptoms: hypotension, tachycardia, nausea, vomiting, dizziness, headache, pyrexia, rigors, and/or chills. These symptoms typically begin within 8 to 24 hours after dosing, and usually resolve within 48 hours of dosing. These signs and symptoms can occur with any dose, though they are more likely to occur with initial doses of 60 mg or higher. When seen, they tend to be more common with the first dose than with subsequent doses.

The complex of tolerability symptoms seen with initial high doses of KZR-616 are similar to those seen with infusion reactions reported for carfilzomib ([KYPROLIS 2018](#)), as well as with systemic inflammatory response syndrome, a clinical syndrome that is a subset of cytokine

release syndrome manifested by at least 2 of the following findings: tachycardia (>90 beats per minute), leukocytosis ($>12 \times 10^9/L$ or $<4 \times 10^9/L$, or $>10\%$ immature [band] forms), tachypnea (respiratory rate of more than 20 breaths per minute or arterial carbon dioxide tension [PaCO₂] of less than 32 mmHg), and fever (temperature of more than 38°C [100.4°F] or less than 36°C [96.8°F]) (Bone 1992). The relative roles of the immunoproteasome versus constitutive proteasomes to these specific events are not known.

In reporting TEAEs related to KZR-616 tolerability, terms such as the NCI-CTCAE terms of ‘infusion-related reaction,’ ‘cytokine release syndrome,’ ‘acute infusion reaction,’ or ‘allergic or hypersensitivity reaction’ should not be used. Instead, each sign or symptom should be recorded as an individual TEAE. If multiple signs or symptoms occur with a given systemic injection-related event, each sign or symptom should be recorded separately with its own level of severity.

Management of these symptoms is described in [Section 6.1.2](#).

9.5.1.2. Thrombotic Microangiopathy

Cases of thrombotic microangiopathy, including thrombocytopenic purpura and hemolytic uremic syndrome, have been described with the nonspecific proteasome inhibitors, bortezomib, carfilzomib, and ixazomib. The clinical presentation of thrombotic microangiopathy typically includes fever, microangiopathic hemolytic anemia (with schistocytes on blood smear), thrombocytopenia, renal failure, purpura, and neurological manifestations. Patients should be monitored for signs and symptoms of thrombocytopenic purpura/hemolytic uremic syndrome. If the diagnosis is suspected, interrupt treatment with KZR-616 and evaluate (refer to [Section 8.1.2](#)). Missed doses should be addressed as per [Section 6.1.3.2](#). If the diagnosis of thrombocytopenic purpura/hemolytic uremic syndrome is excluded, KZR-616 may be resumed. If the diagnosis is confirmed, KZR-616 must be permanently discontinued (refer to [Section 8.2](#)).

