8.1. Study and Individual Patient Stopping Rules

8.1.1. Study Stopping Rules

If any of the following events occur, administration of KZR-616 will be temporarily discontinued until a thorough review of the accumulated safety data is undertaken by the Data Monitoring Committee (DMC) (or appropriate alternative):

- Death in any patient, unless the cause of death is due to obvious alternative etiology
- Unexpected life-threatening event in any patient, unless due to obvious alternative etiology
- Three or more of the same Grade 3 or higher AE (judged by the Investigator, Medical Monitor, or Sponsor's representative), occurring in 20% or more individuals, unless due to obvious alternative etiology
- Any event of thrombotic microangiopathy, thrombocytopenic purpura, or hemolytic uremic syndrome
- Any event that, in the opinion of the Medical Monitor, DMC (or appropriate alternative), or Sponsor, contraindicates further dosing of additional patients

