8.1.2. Individual Patient Stopping Rules

If any of the following events occur, administration of KZR-616 to an individual patient should be discontinued until a review of the accumulated safety data is undertaken by the DMC (or appropriate alternative):

- Any event that fulfills criteria for a study stopping rule, unless due to an obvious alternative etiology (see [Section 8.1.1](#))
- Any event that, in the opinion of the Investigator, Medical Monitor, DMC (or appropriate alternative), or Sponsor, contraindicates further dosing

After such a review, resumption of dosing may be considered at the same or lower dose including consideration for any prophylactic interventions (eg, as per [Section 6.1.2](#))

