8.2. Early Withdrawal of Patients from the Study

Patients must be withdrawn from the study for any of the following reasons:

- Patient request/informed consent withdrawn due to an AE
- Patient request/informed consent withdrawn for any reason other than an AE
- Patient becomes pregnant
- AE (whether or not related to KZR-616) that precludes further participation in the study, in the judgment of the Investigator and/or Sponsor
- Any event of thrombotic microangiopathy, thrombocytopenic purpura, or hemolytic uremic syndrome

Patients may be withdrawn from the study for any of the following reasons:

- Protocol non-compliance, in the judgment of the Investigator and/or Sponsor
- Lost to follow-up
- The Investigator or Sponsor considers that it is in the patient's best interest not to continue participation in the study
- Administrative decision by the Investigator or Sponsor

Patients are free to withdraw from the study at any time without providing reason(s) for withdrawal and without prejudice to further treatment. The reason(s) for withdrawal will be documented in the eCRF. If a patient withdraws consent, all samples obtained will be retained for analysis unless the patient confirms that he or she wishes the samples to be discarded.

Patients withdrawing from study treatment will be encouraged to complete the ETV within 14 days and return for an EOS Visit approximately 12 weeks after receipt of their last dose of KZR-616 to complete the final evaluations according to this protocol, particularly safety evaluations. The aim is to record data in the same way as for patients who complete the study.

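### Section 9.5.1.2 lets dosing resume once thrombocytopenic purpura/HUS, rather than thrombotic microangiopathy (TMA) itself, is excluded, and the resumption sentence in 8.1.2 has no exception matching the mandatory withdrawal in 8.2

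*Combined protocol and SAP*

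**What the plan says.** Five places in the protocol bear on dosing after a TMA.

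- **Section 9.5.1.2** opens with the class: "Cases of thrombotic microangiopathy, including thrombocytopenic purpura and hemolytic uremic syndrome, have been described" with the nonspecific proteasome inhibitors. Its monitoring instruction uses the narrower pair: "Patients should be monitored for signs and symptoms of thrombocytopenic purpura/hemolytic uremic syndrome". On suspicion, the site interrupts KZR-616 and evaluates, with a reference to 8.1.2, and handles missed doses under 6.1.3.2. Then come two outcomes: "If the diagnosis of thrombocytopenic purpura/hemolytic uremic syndrome is excluded, KZR-616 may be resumed", and "If the diagnosis is confirmed, KZR-616 must be permanently discontinued", the latter with a reference to 8.2.
- **Section 8.1.1** lists any TMA, thrombocytopenic purpura or HUS as a study stopping event, on which "administration of KZR-616 will be temporarily discontinued until a thorough review of the accumulated safety data is undertaken" by the data monitoring committee or an appropriate alternative.
- **Section 8.1.2** stops the individual patient for "Any event that fulfills criteria for a study stopping rule, unless due to an obvious alternative etiology". After review it allows dosing to be considered again, at the same or a lower dose.
- **Section 6.1.3.2** lets patients who met the 8.1.2 rules resume after the investigator and Medical Monitor have discussed it.
- **Section 8.2** states "Patients must be withdrawn from the study for any of the following reasons", and one of the listed reasons is "Any event of thrombotic microangiopathy, thrombocytopenic purpura, or hemolytic uremic syndrome".

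**The concern.** TMA is one of two adverse events of special interest named in Section 9.5.1. The withdrawal rule in 8.2 covers the whole class. The condition for re-dosing in 9.5.1.2 names only two members of it, and ruling out two members does not rule out the class. In addition, the general resumption sentence in 8.1.2 reaches every study stopping event, TMA included, without saying that a confirmed TMA is outside it.

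What is at stake is one decision for one patient: whether KZR-616 may be given again after the pause and review. The pause in 8.1.1 is temporary by its own terms, so it does not settle that decision.

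**Working it through.** No arithmetic applies and the plan gives no figure to reproduce. The check applies each section, as worded, to the three states a suspected case can end in.

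| Final diagnosis | 9.5.1.2, literal | 8.1.2 and 6.1.3.2, read alone | 8.2 |
|---|---|---|---|
| All TMA excluded | may resume | may resume | not triggered |
| Thrombocytopenic purpura or HUS confirmed | permanent stop, cites 8.2 | may resume | must withdraw |
| TMA confirmed, neither of the two | may resume | may resume | must withdraw |

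**First row.** No conflict. This row also shows why 8.1.2 needs a resumption route at all: it serves every stopping event, including suspicions that come to nothing.

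**Second row.** The TMA-specific section and 8.2 agree that dosing ends. The mismatch lies only in the general sentence of 8.1.2. That section takes in the 8.1.1 events unless there is an obvious alternative etiology, then allows resumption without setting these diagnoses apart or pointing to 8.2. Section 6.1.3.2 takes its patients from 8.1.2 and so inherits the gap. It does cite 8.2, but for recording discontinuation and for the Early Termination Visit, not to limit resumption. Because one clause borrows the scope of the other, they are better counted as close to one permission than as two.

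**Third row.** Here 9.5.1.2 itself departs from 8.2. The resumption sentence is satisfied because the two named diagnoses have been excluded. The sentence on confirmation speaks of the diagnosis just discussed, which is again the pair, so it does not clearly reach this patient. Section 8.2 does reach the patient, because it lists TMA separately from the pair.

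**Which text governs.** Section 8.2 says must; the others say may. A site that withdraws the patient breaches nothing. The conflict becomes real only if someone uses a permission without also reading 8.2.

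**The case against.** The strongest reply is that the protocol already puts the steps in order. In 9.5.1.2, Sections 8.1.2 and 6.1.3.2 are cited at the suspicion and interruption stage, and 8.2 is cited once the diagnosis is confirmed. On that reading a specific, mandatory rule controls a general, discretionary one, and a patient who must leave the study is not a candidate for re-dosing. This stands for thrombocytopenic purpura and HUS, and it limits the point considerably.

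A second reply is that the pair is shorthand for TMA: the section is headed TMA, the clinical picture described is that of TMA, and no other form is named anywhere in the documents. This is plausible, and if accepted it closes the gap in 9.5.1.2. It is not secured, because 8.1.1 and 8.2 both list TMA alongside the two diagnoses as a separate item. It also leaves the missing exception in 8.1.2 untouched.

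A third reply is that several safeguards stand in the way of re-dosing: the study-wide pause and safety review, the 24-hour reporting, and the Medical Monitor discussion. This is correct and is why the practical risk is small.

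A reader might go further and infer that the protocol lets patients with confirmed TMA in general go back on drug through three independent routes. The documents do not support that. For the two named diagnoses 9.5.1.2 requires a permanent stop, 8.2 is mandatory for all TMA, and 6.1.3.2 depends on 8.1.2 for its scope.

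**Conclusion.** The point holds as a minor safety-wording inconsistency. It has two parts: the resumption condition in 9.5.1.2 is narrower than the withdrawal rule in 8.2, so that a TMA that is neither thrombocytopenic purpura nor HUS could literally be re-dosed; and the general resumption sentence in 8.1.2, with 6.1.3.2 following it, has no exception for confirmed cases.

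The first part assumes that the paired diagnoses in 9.5.1.2 mean what they say and are not shorthand. The second does not need that assumption. The size cannot be expressed as a rate, because the documents give none for TMA. Any effect is confined to individual patients among the up to 24 planned (Section 4.1). No endpoint, analysis set or summary is affected.

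**What to change.** Three wording changes bring the resumption texts into line with 8.2.

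1. In the monitoring, exclusion and confirmation sentences of 9.5.1.2, replace the paired diagnoses (or the reference back to them) with: *thrombotic microangiopathy (including thrombocytopenic purpura and hemolytic uremic syndrome)*. Dosing then resumes only when TMA itself has been excluded.
2. In 8.1.2, after the resumption sentence, add: *Resumption does not apply to confirmed thrombotic microangiopathy, thrombocytopenic purpura, or hemolytic uremic syndrome, for which Section 8.2 requires withdrawal.*
3. In 6.1.3.2, add to the sentence that allows dosing to resume: *subject to the exception in Section 8.1.2*.

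Sections 8.1.1 and 8.2 need no edit. The cost is three reworded sentences, one new sentence and one clause, with no new procedure, data collection or analysis.

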9.6. Unexpected Adverse Reactions

9.6.1. Definition of an Unexpected Adverse Reaction

An unexpected adverse reaction is any untoward and unintended response that is related to the administration of KZR-616 at any dose that is not consistent with the applicable product information (eg, the Reference Safety information of the KZR-616 Investigator’s Brochure).

All suspected unexpected serious adverse reactions (SUSARs) will be subject to expedited reporting. The Sponsor or designee shall ensure that all relevant information about a SUSAR that is fatal or life-threatening is reported to the relevant competent authorities and IRB/IEC within 7 days after knowledge by the Sponsor of such a case, and that relevant follow-up information is communicated within an additional 8 days. All other SUSARs will be reported to the relevant competent authorities and IRB/IEC within 15 days after knowledge by the Sponsor of such a case. All Investigators should follow up SUSARs until the event is resolved or until, in the opinion of the Investigator, the event is stabilized or determined to be chronic. Post study SUSARs that occur after the patient has completed the clinical study must be reported by the Investigator to the Sponsor.

9.7. Data Monitoring Committee

A study-specific DMC or other appropriate review committee may be used to enhance the safety and integrity of the study data for interim safety monitoring. If such a committee is used, the specific responsibilities and composition will be outlined in a separate DMC Charter.

10. STATISTICAL ANALYSES

This study is descriptive in nature, and no formal hypothesis testing will be performed. No formal statistical sample size estimation has been performed, since the number of patients in this study is determined by the number of patients who completed Study KZR-616-003 and enrolled in this study. Descriptive statistics, including the numbers and percentages for categorical variables; and the numbers, means, standard deviations (SD), medians, minimums and maximums for continuous variables will be provided by treatment group, by indication (DM, PM), and overall.

The number and percentage of patients who experience TEAEs, SAEs/death, AEs leading to treatment/study discontinuation, and treatment modification/delay due to AE(s) will be summarized by treatment group and overall. The number and percentage of patients experiencing any TEAE(s), overall, and by system organ class (SOC) and preferred term and by grade will be tabulated.

Continuous measures in laboratory, vital sign, ECG, and efficacy data will be summarized descriptively (mean, median, SD, and minimum and maximum values) by treatment group and overall and will be summarized by protocol-specified time point along with a summary of change from baseline at each time point. Changes in physical examinations will be listed for each patient and described. In addition, 95% confidence intervals may be provided to describe some continuous efficacy data.

Patient listings will be provided to support these summaries.

PK analyses will include determination of plasma levels of KZR-616 including C_{max} , T_{max} , and AUC.

Full Analysis Set (FAS): The FAS for summaries of efficacy endpoints will include all patients who receive KZR-616 in this study and have baseline and any post-baseline data. All observed data will be included in the statistical summaries. No missing data will be imputed except as pre-defined in the SAP.

Per Protocol (PP): A PP population may be used to analyze select efficacy endpoints, and will be based on KZR-616 exposure (time on treatment) and protocol deviations. The decision to summarize a PP population will be made prior to database lock.

Safety Population: The safety population will include all patients enrolled who received at least one dose of KZR-616, and will be the population used for the analysis of safety. Adverse event data will be coded to system organ class and preferred term using Medical Dictionary for Regulatory Activities (MedDRA; Version 19.1 or later).

Data will be summarized for the following groups of patients based on the sequence of treatments received in Study KZR-616-003:

Group 1: Arm A (KZR-616:Placebo) from Study KZR-616-003 beginning on Day 1 (first dose of KZR-616) through the end of Study KZR-616-003E

Group 2: Arm B (Placebo:KZR-616) from Study KZR-616-003 beginning on Week 16 (first dose of KZR-616) through the end of Study KZR-616-003E

Groups 1 and 2 combined: from the first dose of KZR-616 in KZR-616-003 through the end of KZR-616-003E

Group 3: Arm B2: Patients receiving KZR-616 from Weeks 16-32 in KZR-616-003 followed by KZR-616 in OLE throughout KZR-616-003E, to evaluate patients who continuously received KZR-616 from KZR-616-003 through KZR-616-003E

Groups 1 and 2 are being assessed for any differences due to the intervening placebo treatment period in Group 1. The rationale for combining Group 1 and Group 2 is to encompass all KZR-616 treatment, and the rationale for assessing Group 3 is to encompass all continuous KZR-616 treatment.

Further details of the statistical methodology, including methods for handling missing data and early withdrawals, will be provided in an SAP that will be finalized prior to database lock. As KZR-616-003E is an open-label extension study, endpoints in addition to those described in [Section 2.2](#) may be conducted as described in the final SAP.

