2.2. Study Endpoints

2.2.1. Efficacy Endpoints

- Mean change in TIS over time for all patients, for patients with DM only, for patients with PM only, and for patients with a myositis-associated antibody or myositis-specific antibody at the Screening Visit of Study KZR-616-003
- Proportion of patients by TIS response (minimal response = TIS \geq 20, moderate response = TIS \geq 40, major response = TIS \geq 60)
- Proportion of patients meeting IMACS definition of improvement (DOI) over time for patients with baseline core set measures as ascertained at the beginning of KZR-616-003
- Mean change and mean percentage change over time in the IMACS individual CSAMs and CSDMs, stratified by all patients and patients with myositis-associated or myositis-specific antibody at the Screening Visit of Study KZR-616-003
- Mean change over time in the Cutaneous Dermatomyositis Disease Area and Severity Index (CDASI) for all patients with DM, and for patients with DM who have active skin manifestations at baseline of Study KZR-616-003E
- Mean change over time in the MDI
- Mean change over time in muscle enzymes
- Change in proportion and dose of corticosteroid and non-corticosteroid immunosuppressants during Study KZR-616-003E for all patients, and for patients taking corticosteroids or non-corticosteroid immunosuppressants at baseline of Study KZR-616-003E
- Percentage of patients requiring additional medication for myositis treatment during Study KZR-616-003E
- Mean change over time in the EuroQol 5-dimension 5-level (EQ-5D-5L)
- Additional exploratory endpoints (Physician Global Impression of Change [MDGIC], Functional Index-2 [FI-2], Patient Global Impression of Change [PGIC], and Peak Pruritis Numerical Rating Scale [NRS]) will be assessed at multiple time points

As KZR-616-003E is an open-label extension study, additional exploratory endpoints may be conducted, and will be described in the final statistical analysis plan (SAP). Efficacy endpoints may include treatment periods that include data from Study KZR-616-003 based on treatment sequence in that study. See [Section 10](#) for additional details of statistical analyses.

All endpoints, except where noted, will include analyses of all patients, those with DM only, and those with PM only.

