3. STUDY DESIGN

3.1. Type and Design of Study

This is an open-label study to evaluate the long-term efficacy and safety of KZR-616 in patients with active PM or DM who completed the double-blind treatment period of Study KZR-616-003, up to and including the Week 32 Visit, prior to the first dose of open-label KZR-616.

The study design schema is presented in [Figure 1](#).

Patients will be evaluated for eligibility according to the entry criteria (see [Section 4](#)) at, or within 8 weeks after, the Week 32 Visit (ie, the End of Treatment [EOT] Visit [Visit 34]) of Study KZR-616-003. Informed consent may be signed prior to the Week 32 Visit of Study KZR-616-003, and must be signed prior to any study-related activity in KZR-616-003E. For patients who are eligible and willing to enroll in the open-label extension study, the KZR-616-003 Week 32 Visit may also serve as Visit 1 (Day 1) for the open-label extension study. Assessments at this visit performed as part of Study KZR-616-003 will be used as baseline values for the extension study; therefore, these assessments must be performed prior to the first dose of open-label KZR-616 (see [Figure 1](#)).

[figure not shown]
All patients will receive a SC injection of 30 mg KZR-616 at Visit 1 (Day 1), followed by weekly SC injections of 45 mg KZR-616 up to a maximum of 96 weeks. Study drug administration will end for all patients in Study KZR-616-003E when the last patient enrolled has completed 48 weeks of dosing. Patients will have a final follow-up visit 12 weeks after their last dose of KZR-616 (End of Study [EOS] Visit), for a maximum potential length of participation of 108 weeks.

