9.1.5. Follow-up of Adverse Events

Adverse events are intended to be collected according to the procedures outlined above from the time of informed consent and continuing for 30 days following the last dose, or the EOS Visit, whichever occurs later.

All Investigators should follow up patient AEs until the event is resolved or until, in the opinion of the Investigator, the event is stabilized or determined to be chronic. Details of AE resolution must be documented in the eCRF.

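### AE incidence and additional myositis medication are planned only as crude percentages, although planned follow-up can differ by enrollment date and Group 1's window is 16 weeks longer than Group 2's

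*Combined protocol and SAP*

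**What the plan says.** Section 3.1 sets a ceiling on dosing, "followed by weekly SC injections of 45 mg KZR-616 up to a maximum of 96 weeks", and a common stop: "Study drug administration will end for all patients in Study KZR-616-003E when the last patient enrolled has completed 48 weeks of dosing". A follow-up visit comes 12 weeks after the last dose. Section 9.1.5 collects adverse events "from the time of informed consent and continuing for 30 days following the last dose, or the EOS Visit, whichever occurs later".

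Section 10 gives the AE summary as "The number and percentage of patients who experience TEAEs, SAEs/death, AEs leading to treatment/study discontinuation", by treatment group and overall, with TEAEs also tabulated by system organ class, preferred term and grade. Section 2.2.1 lists this endpoint: "Percentage of patients requiring additional medication for myositis treatment during Study KZR-616-003E".

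Section 10 also defines groups by parent-study sequence. Group 1 (KZR-616 then placebo) is summarized "beginning on Day 1 (first dose of KZR-616) through the end of Study KZR-616-003E", and Group 2 (placebo then KZR-616) "beginning on Week 16 (first dose of KZR-616) through the end of Study KZR-616-003E". The two are to be assessed for differences due to the placebo period in Group 1.

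Exposure appears in Section 10 only as a basis for the optional per-protocol efficacy set. Further methods, including those for missing data and early withdrawals, are left to a later SAP, which is not among the documents.

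**The concern.** A cumulative percentage answers a clear question only if everyone is observed for about the same time. Here the design can make observation time unequal in two ways.

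First, an early enrollee may be dosed and observed for longer than the last enrollee, so the overall percentage depends partly on how enrollment was spread. Second, Group 1's window exceeds Group 2's by 16 weeks even when extension time is equal. The additional weeks are Group 1's parent-study placebo period, so planned KZR-616 time does not differ.

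Long-term safety is one of the study's two objectives. As written, a higher AE percentage in Group 1 could reflect only its longer window, and the overall figure could move with accrual while the underlying risk stayed the same. The additional-medication endpoint shares the first problem. It does not share the second, because it counts only events during the extension.

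**Working it through.** **Inputs from the protocol**
- Dosing cap 96 weeks; common stop when the last enrollee has 48 weeks (Section 3.1).
- Follow-up 12 weeks after last dose (Section 3.1); AE collection to the later of 30 days or the EOS Visit (Section 9.1.5). The EOS Visit is later.
- Parent-study time in the window: 32 weeks for Group 1, and 32 − 16 = 16 weeks for Group 2 (Section 10).
- Up to 24 patients (Section 4.1).

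**The plan's own figure.** Maximum participation is 96 + 12 = 108 weeks, as Section 3.1 states. Table 1 agrees: (750 − 666)/7 = 12 weeks from EOT to EOS.

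**Planned dosing.** For a patient enrolled L weeks before the last one, planned dosing is min(96, 48 + L), and AE observation in the extension is that plus 12. The limits are 48 + 12 = 60 and 96 + 12 = 108 weeks. The enrollment spread is not in the documents. For 24 evenly spaced enrollments (an assumption):

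| Spread (weeks) | Dosing min / mean / max (weeks) |
|---|---|
| 0 | 48 / 48 / 48 |
| 24 | 48 / 60 / 72 |
| 48 | 48 / 72 / 96 |
| 72 | 48 / 79.7 / 96 |

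**Effect on a crude percentage.** Assume a constant hazard h and no withdrawal, so risk(t) = 1 − exp(−ht). With an assumed 48-week risk of 20%, h = −ln(0.8)/48 = 0.00465 per week. Then:
- 60 weeks: 1 − exp(−0.2789) = 24.3%
- 108 weeks: 1 − exp(−0.5021) = 39.5%

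Other assumed 48-week risks give, at 60 versus 108 weeks: 5%, 6.2% versus 10.9%; 10%, 12.3% versus 21.1%; 30%, 36.0% versus 55.2%; 50%, 58.0% versus 79.0%.

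Those pairs are the limits for single patients. The study-level percentage is the mean of 1 − exp(−h(dosing + 12)) over the 24 patients. At the 20% assumption it is 24.3%, 28.4%, 32.2% and 34.5% for spreads of 0, 24, 48 and 72 weeks. The exposure-adjusted rate is the same at every spread: 100 × 52.18 × h = 24.3 per 100 patient-years (numerically equal to the 60-week percentage by coincidence).

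**Groups 1 and 2, same hazard, minimum extension dosing.**
- Group 1: 32 + 48 + 12 = 92 weeks; 1 − exp(−0.4277) = 34.8%
- Group 2: 16 + 48 + 12 = 76 weeks; 1 − exp(−0.3533) = 29.8%

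The 5.0-point difference comes only from window length. Section 6.1 allows up to 8 weeks between the parent Week 32 Visit and the first extension dose. That gap is left out, and could lengthen either window.

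**The case against.** - **The SAP may add time-based measures.** It may. But the topics Section 10 names for it are missing data and early withdrawals, and nothing commits it to patient-time or time-to-event estimates. Because it is finalized only before database lock, there is still room to act.
- **The stop rule need not produce a twofold range.** This stands. A reader might infer that dosing will run from 48 to 96 weeks; the documents give only the rule and no enrollment dates. The group-window difference does not depend on enrollment spread.
- **A constant hazard fits some expected events poorly.** This also stands. Section 9.5.1.1 says tolerability symptoms tend to be more common with the first dose. For such events the crude percentage hardly depends on follow-up length, and a single rate per patient-year falls merely because follow-up lengthens.
- **Entry requires completing the parent study through Week 32.** An enrolled patient could therefore hardly have left the parent study because of an AE. The 92-versus-76-week illustration should not be applied to AE discontinuation, and parent-study time should not enter a rate for it.
- **Other safety data are unaffected.** Laboratory, vital-sign and ECG measures are summarized by time point and listings are planned, so the gap is confined to cumulative proportions.
- **Early withdrawal.** A reader might infer that an early leaver will be counted as not needing additional medication. The documents leave that handling to the SAP. Nor does permanent discontinuation for an AE necessarily end observation, since Section 6.1.3.2 continues the planned assessments.
- **Comparison with 16-week parent-study periods.** A reader might see this as threatened too, but the documents plan no such comparison.

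**Conclusion.** The point holds as a gap in the descriptive analysis. AE incidence and additional medication have no time-based measure, while planned follow-up may vary with enrollment date and does differ by 16 weeks between two groups the protocol intends to assess against each other.

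The enrollment-date effect ranges from nothing, if all enroll together, to the 24.3%-versus-39.5% contrast between individual patients at the two limits. The group effect is about 5 percentage points under the stated illustration. Both sizes rest on a constant hazard and an assumed 20% risk at 48 weeks, and both overstate the effect for events concentrated at first doses.

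The study is uncontrolled, tests no hypothesis and has at most 24 patients, so what is at stake is how the figures are read, not an error rate. The change should be made, but the study does not fail without it.

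**What to change.** Keep n (%) and add the following to Section 10 and the SAP:

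1. Patient-years at risk and exposure-adjusted first-event rates with exact Poisson 95% confidence intervals for TEAEs, SAEs and AESIs, by group. Show events and time in Group 1's placebo period separately from KZR-616 time.
2. TEAE incidence by 24-week interval with numbers at risk, because one overall rate misleads for front-loaded events.
3. Cumulative incidence at Week 48 of the extension, counted from the first extension dose, for AE discontinuation and for first additional myositis medication. The stop rule lets every patient reach Week 48. Censor administrative stops. Report early withdrawals separately, with a sensitivity analysis, because they may be informative.

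Confirm that start dates of added myositis medication are captured: the non-exhaustive list in Section 6.2 does not name them. AE onset dates are already required by Section 9.1.6.

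The cost is revised text and a few extra tables. With at most 24 patients the intervals will be wide, and the added estimates should be presented as descriptive.
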